## **GCP Compliance Statement:**

This trial will be conducted in compliance with the protocol, the principles that have their origin in the Declaration of Helsinki and all applicable regulatory requirements

## 1. SYNOPSIS

Trial Identifying Numbers	IRAS: 282405					
, 5	EudraCT: 2020-001449-38					
Chief Investigator	[name]					
Lead Sponsor	Chelsea and Westminster Hospital NHS Foundation Trust					
	Research and Development,					
	[name],					
	[name],					
	[name]					
Co-Sponsor	NEAT ID Foundation					
- CC 3poilise.	Registered address:					
	[name]					
	Administrative office:					
	[name]					
Data Management	Clinical Informatics Team					
Data Management	Research Organisation (KC) Ltd. (ROKC)					
	[name]					
Pharmacovigilance	Pharmacovigilance Team					
rnamiacovignance	Research Organisation (KC) Ltd. (ROKC)					
	[name]					
Manitaring	Clinical Risk Based Monitoring Team					
Monitoring						
	Research Organisation (KC) Ltd. (ROKC)  [name]					
Lood Supragu Contact	[name]  [name]					
Lead Sponsor Contact						
	Research Delivery and Operations Manager					
	Chelsea and Westminster Hospital NHS Foundation Trust [contact] [name]					
Childry Combons						
Study Contact	[name]					
	Respiratory Research Fellow					
	Royal Brompton and Harefield NHS Foundation Trust					
6. 1. 7.11	[contact]					
Study Title	A Randomised Controlled Trial of Early Intervention in					
	Patients HospItalised with COVID-19: Favipiravir and					
01 . =::1	staNdard care vErsEs Standard CaRe					
Short Title	PIONEER					
Name of Active Ingredients	Favipiravir					
Primary Objective	To determine whether early intervention with Favipiravir					
	improves the time to significant improvement in clinical					
	status in patients with COVID-19 infection					
Secondary Objectives	To assess whether early intervention with Favipiravir					
	improves mortality in patients with COVID-19 infection					
	To determine whether early intervention with Favipiravir					
	•					

	 				
	reduces resource utilisation in patients with COVID-19 infection				
	To explore whether early intervention with Favipiravir attenuates the excessive inflammatory cytokine response in patients with COVID-19 infection				
Exploratory Objectives	To identify prognostic markers indicating the need for early intervention with Favipiravir in patients with COVID-19 infection  To assess the pharmacokinetics and pharmacodynamics of Favipiravir				
Study Type	Interventional Cohort: prospective, open-label, multi-centre randomised control trial  Data Cohort: Collection of clinical data on all newly admitted patients with suspected or confirmed COVID-19 infection				
Methodology	Eligible participants with suspected or proven COVID-19 infection will be randomised 1:1 to receive Favipiravir or standard of care  Data Cohort: Collection of clinical data on all newly admitted patients with suspected or confirmed COVID-19 infection (UK only)  Future Research: Blood, urine, nasopharyngeal, sputum samples will be collected from trial participants, with consent for use in future research				
Participants	Patients hospitalised with suspected or proven COVID-19 infection				
Planned Sample Size	500 globally				
Planned Treatment Duration	10 Days				
Planned Study Duration	October 2021				
First Enrolment Date (actual)	1 st May 2020				
Treatment Regimen, Dose and Route of Administration	Arm 1: Product: Favipiravir Dose Day 1: 1800mg BD PO Dose Day 2-10: 800mg BD PO + Standard of care Arm 2:				
	Standard of care				
Inclusion Criteria	
 
Adult participants: Signed informed consent or documented and witnessed oral informed consent
 
New admission to hospital for period expected to last ≥ 1 night
 
Suspected or confirmed COVID-19 infection
 
Patients are suspected of COVID-19 infection if they have the
 
				

	
 
Influenza like illness (fever ≥37.8°C or patient reported history of fevers and at least one of the following respiratory symptoms, which must be of acute onset: persistent cough, hoarseness, nasal discharge or congestion, shortness of breath, sore throat, wheezing or sneezing).
 
And
 
Finding from either a chest x-ray or CT suggestive of Covid-19 infection.
 
And
 
Alternative causes are considered unlikely and therefore in view of the investigator, admission of the patients to hospital is primarily attributable to symptoms of COVID-19 disease.
 

	
 
4. For women to be eligible to enter and participate in the study they should be non-child-bearing: 
 
of potential defined as either post-menopausal (12 months of spontaneous amenorrhea and ≥ 45 years of age) or physically incapable of becoming pregnant with documented tubal ligation, hysterectomy or bilateral oophorectomy or,
 
or if child-bearing potential have a negative pregnancy test at screening and agrees to remain sexually abstinent or use a method of contraception with a failure rate of < 1% per year as indicated in Appendix B during the treatment and for a period of 7 days after the last dose. Hormonal contraceptive methods must be supplemented by a barrier method.
 
 
 
5. Men who are sexually active must use an adequate
 

	method of contraception as listed in Appendix B, for a period of at least 7 days after the last dose.
Exclusion Criteria	
 
Pregnant or breast feeding, due to potential teratogenicity (Negative pregnancy test if appropriate)
 
Hepatic impairment – (AST or ALT > 3.5 x upper limit of normal)
 
Presently enrolled in an interventional drug study
 
Unable to take medication via the oral or nasogastric
 

	route 5. Known sensitivity to Favipiravir

## 3. STUDY MILESTONES

Milestones	Planned Date
Study Start	1 st May 2020 (actual date)
Study End	October 2021
Study Report	October to December 2021

## 4. ABBREVIATIONS

AE	Adverse Event
AR	Adverse Reaction
ADR	Adverse Drug Reaction
BD	Twice daily
CA	Competent Authority
CI	Chief Investigator
COVID-19	Corona virus
CRF	Case Report Form
CWFT	Chelsea and Westminster Hospital Foundation Trust
DSMB	Data Safety Monitoring Board
EC	Ethics Committee
ЕСМО	Extracorporeal Membrane Oxygenation
EC50	Concentration of a drug which produces 50% of the maximal possible effect
ECRF	Electronic Clinical Research form
GCP	Good Clinical Practice
GP	General Practitioner
ICF	Informed Consent Form
IRB	Institutional review board
NEWS2	National Early Warning System 2
NHS	National Health Service
NRES	National Research Ethics Service
OD	Once daily
PI	Principal Investigator

PIS	Participant/ Patient Information Sheet			
PVMP	Pharmacovigilance Management Plan			
R&D	NHS Trust R&D Department			
REC	Research Ethics Committee			
SAE	Serious Adverse Event			
SERF	afety Event Reporting Form			
SUSAR	Suspected Unexpected Serious Adverse Event			
SOP	Standard Operating Procedure			
TMG	Trial Management Group			
WOCBP	Woman of Child-Bearing Potential			

#### 5. BACKGROUND AND RATIONALE

Coronaviruses are enveloped non-segmented positive-sense RNA family viruses, belonging to the family Coronaviridae and are broadly distributed in humans and other mammals.(1) Whilst the majority of human coronavirus infections are mild, a novel coronavirus first identified in December 2019 and designated SARS-CoV-2, has caused the global outbreak of respiratory illness, termed COVID-19.(2) Pandemic status was attributed in March 2020, with in excess of 900,000 cases and 45,000 deaths reported worldwide.(3) COVID-19 causes a spectrum of respiratory illnesses, ranging from self-limiting respiratory symptoms, pneumonia, respiratory failure and death.(2, 4) Currently there are no licensed treatments for COVID-19 and whist vaccinations are being developed, the re-purposing of existing drugs is an immediate option. High mortality rates in some regions have been related to the saturation of healthcare resources, such as intensive care beds and ventilators, demonstrating the clear and unmet need for an early intervention that reduces the intense utilisation of such facilities.(5)

Favipiravir is a pyrazinecarboxamide derived, nucleic acid analogue which selectively targets the RNA Dependent RNA Polymerase utilised in viral RNA synthesis, without interfering with host RNA and DNA polymerase activity.(6) Favipiravir has demonstrated broad spectrum activity against multiple families of RNA viruses including a wide range of types and subtypes of influenza viruses.(6) A small nonrandomised study in China in patients with Covid-19 infection demonstrated increased viral clearance, and an improved time to resolution of symptoms and changes demonstrated on chest imaging. (7) Currently, the therapy is not licensed in the UK but has been in use in Japan since 2014. (8) Favipiravir is currently undergoing FDA approval for uncomplicated influenza in the USA, whereby Phase 3 studies (NCT02008344, NCT02026349) investigated 1800 mg BD on day 1, followed by 800 mg BD days 2-5 vs placebo. As part of these works, 1472 subjects received this dosage and 3160 received at least one dose, with no serious drug related adverse events identified. Subjects in the FDA studies achieved "undetectable virus" status significantly faster than the subjects on placebo.(9)

#### 6. OBJECTIVES AND OUTCOME MEASURES & ENDPOINTS

## 6.1. Primary Objective

• To determine whether early intervention with Favipiravir improves the time to significant improvement in clinical status in patients with COVID-19 infection

## 6.2. Secondary Objective

- To assess whether early intervention with Favipiravir improves mortality in patients with COVID-19 infection
- To determine whether early intervention with Favipiravir reduces resource utilisation in patients with COVID-19 infection
- To explore whether early intervention with Favipiravir attenuates the excessive inflammatory cytokine response in patients with COVID-19 infection

## 6.3. Exploratory Objectives

• To identify prognostic markers indicating the need for early intervention with Favipiravir in patients with COVID-19 infection

## 6.4. Outcome Measures & Endpoints

Objectives	Outcome Measures/Endpoints
Primary Objective To determine whether early intervention with Favipiravir improves the time to significant improvement in clinical status in patients with COVID-19 infection	Time from randomisation to a sustained clinical improvement (maintained for 24 hours) by two points on a seven-category ordinal scale or to discharge, whichever occurs first(10)  The seven-category ordinal scale:  1: Not hospitalised with resumption of normal activities  2: Not hospitalised, but unable to resume normal  3: Hospitalised, not requiring supplemental oxygen  4: Hospitalised, requiring supplemental oxygen  5: Hospitalised, requiring nasal high-flow oxygen therapy, non-invasive mechanical ventilation or both  6: Hospitalised, requiring ECMO (Extra-corporal membrane oxygenation), invasive mechanical ventilation or both  7: Death(10)

## **Secondary Objectives**

To assess whether early intervention with Favipiravir improves mortality in patients with COVID-19 infection

To determine whether early intervention with Favipiravir reduces resource utilisation in patients with COVID-19 infection

To explore whether early intervention with Favipiravir attenuates the excessive inflammatory cytokine response in patients with COVID-19 infection

- Clinical status as assessed with the seven-category ordinal scale at day 7 and day 14 (postrandomisation)(19)
- 2. Change in clinical status as assessed with the sevencategory ordinal scale at day 7 and day 14 (postrandomisation) relative to baseline(10)
- 3. All-cause in-hospital mortality
- Time to clinical response defined as:
   Time to 2 point reduction (maintained for 24 hours) in total NEWS2 (National Early Warning Score 2) compared to baseline NEWS2 taken at Randomisation(11)
- 5. Time to 2 point reduction (maintained for 24 hours) in the NEWS2 (National Early Warning Score 2) component compared to baseline NEWS2 taken at Randomisation for each of the following:
  - Temperature
  - Heartrate
  - Respiratory rate
  - Oxygen saturations(11),
- 6. Number of participants requiring intensive care admission
- 7. Duration of intensive care admission
- 8. Number of participants requiring mechanical ventilation
- 9. Duration of mechanical ventilation
- Number of participants requiring non-invasive ventilation, continuous positive airways pressure or high-flow oxygen via (Optiflo®, Airvo system or equivalent)
- 11. Percentage of progression in supplemental oxygen requirement at day 7
- 12. Number of participants readmitted to hospital (all-
- 13. Proportion of patients with culture confirmed bacterial or fungal infection
- 14. Changes in host inflammatory profiles at postrandomisation time points, relative to baseline

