#### 7. TRIAL DESIGN

The study is an open-label, two arm, multi-centre randomised controlled clinical trial, to investigate the clinical effectiveness, safety, and resource utilisation of early treatment intervention in patients admitted to hospital with a suspected or proven COVID-19 infection. Subjects will be randomised 1:1 to one of two arms to receive:

- Arm 1: Favipiravir + standard of care
- Arm 2: Standard of care

The study treatment duration will be 10 days for each participant. If a participant recovers sufficiently to be discharged home before day 10, favipiravir will be supplied and the regimen completed as an outpatient.

Samples will be collected at three timepoints: baseline, between days 5 to 10 and days 14 to 28 (see section 9.4). In such instances where participants recover sufficiently to be discharged home and are not in hospital at the latter sample collection timepoints, they will be invited to return to facilitate this (provided that they are well enough and maximally twice).

For further information on activities at visits and schedule see Section 8.

Participants will exit the study at day 28 or if they become deceased.

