#### 8.8. Duration of Involvement

The duration of study treatment is 10 days and participants will remain on the study for 28 days from randomisation.

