#### 10.2. Inpatient Data Collection

Whilst patients are hospitalised all routine data, including laboratory test results, procedures and medication will be collected as necessary, as part of the trial from day 0 to day 28 or until discharge, whichever is sooner. Change in ordinal score lasting >24 hours will be recorded. If patients are readmitted within the 28-day period, data will also be collected from this second admission until 28 days post-study commencement.

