## 10.3. Follow-Up Data Collection

For participants discharged prior to day 10, a member of the research team will telephone and conduct a short interviews to collect the following information:

- Study drug compliance Drug accountability data will be collected during the Trial. Any deviation from protocol-directed administration is to be reported.
- AEs and SAEs
- Concomitant medications
- Overall health
- Ordinal score (including at discharge) collected as a snapshot

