## 12.6. Collecting and Recording AE and SAE

- All non-COVID-19 associated AEs and SAEs, whether or not they are related to the study intervention or protocol defined procedures must be documented in the patients' medical notes and eCRF. If no diagnosis is available, the Investigator should record each sign and symptom as individual AEs.
- The site will enter the AEs and SAEs into the eCRF as soon as it is known to the Investigator or sub investigator. The eCRF must be updated as soon as additional information is made available to the investor or sub investigator. If the electronic system is unavailable for more than 24 hours, then the site will use the paper form
- Reportable SAEs as defined above will be reported to the Co-Sponsor within 24 hours of the study team becoming aware of the event. SAE details will be included in the Safety Event Report Form (SERF) and the SERF emailed to [contact] or faxed to [name].
- The AEs and SAEs reporting period will be from participant consent until 28 days after randomisation.
- Pregnancy will be also subjected to the same reporting rules of SAE. Pregnancy details will be included in the SERF and the SERF emailed to [contact] or faxed to [name] within 24 hours of the study team becoming aware of the pregnancy.
- All AEs and SAEs will be followed up until resolved or the participant's participation in the study ends (i.e. until the final CRF is completed for that participant).
- When an AE/SAE occurs, it is the responsibility of the investigator or sub investigators to review all clinical information relating to the event.
  - The investigator or sub investigator will attempt diagnose the event based on direct examination and/or other clinical information.
  - The principle investigator must confirm within the SERF the causality assessment with the study drug. If the SAE is assessed as possibly related, probable related or definitely related, the principal investigator must also confirm the event expectedness versus the Reference safety information (refer to section 12.10).
- The Investigator must record follow-up information (related to the reported event) by updating the patient's medical records and the appropriate forms in the (e)CRF. The worst-case severity and seriousness of an event must be kept throughout the trial.

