#### 13. STATISTICS AND ANALYSIS

### 13.1 Description of Statistical Methods

The two arms (Favipiravir vs Standard of Care) will be compared with time-to-event analysis using a competing-risks survival regression based on Fine and Gray's proportional subhazards model. All analysis will be performed on an intention to treat basis.

Patient improvement will be monitored for 28 days or until death. It is not expected that any patient will be lost to follow-up, even if discharged home. Kaplan-Meier plots will be constructed showing the probability of survival in each treatment group. Schoenfeld Residuals will be plotted and tested over time to examine the assumption of proportional hazards; with a restricted mean survival time analysis (RMST) as an alternative method for analysis for the proportional hazards assumption is not met.

Similarly, patients who discontinued the clinical trial or administration of the study drug due to worsening of symptoms/lack of efficacy (including patients who switched to rescue therapy) but remain alive will be handled as cases right-censored as of day 28, with no clinical improvement.

Additional secondary analysis of the primary outcome will be undertaken that adjust for, or involves a sub-set of patients, and examines the effect of

- (a) country of recruitment
- (b) time from onset of symptoms (median split)
- (c) limited to those patients with confirmed SARS-COV-2 infection
- (d) by high or low (median split) viral load.
- (e) early or late during recruitment to the study to examine improves in clinical care and understanding.

Other secondary analysis have been pre-specified in the statistical analysis plan and listed on clinical trials.gov. Differences between the two trial arms will be compared by standard and appropriate statistical tests.

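### The only mortality endpoint counts in-hospital deaths although participants are followed to day 28, and deaths at home after discharge are not reliably ascertained

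*Protocol*

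**What the plan says.** The objective in Protocol 6.4 is "To assess whether early intervention with Favipiravir improves mortality in patients with COVID-19 infection", with no restriction by place. The one mortality endpoint listed against it, item 3 of the secondary endpoints, is "All-cause in-hospital mortality", and it carries no stated time horizon.

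Follow-up is meant to last four weeks. Section 8.8 says "participants will remain on the study for 28 days from randomisation", and section 7 says "Participants will exit the study at day 28 or if they become deceased".

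Data collection is narrower:

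- Section 10.2 collects routine data "from day 0 to day 28 or until discharge, whichever is sooner". It adds that data from a readmission are collected up to day 28.
- Section 10.3 begins "For participants discharged prior to day 10, a member of the research team will telephone" and gives no day for the call.
- Section 10.4 asks those discharged before day 14 to return for sampling in days 14 to 28, and those discharged before day 5 also in days 5 to 10, if they are well enough.
- Section 9.4 asks for bloods from discharged patients at the day 5-10 and day 14-28 visits.
- Section 12.6 says "The AEs and SAEs reporting period will be from participant consent until 28 days after randomisation", but sections 12.2 and 12.4 define adverse and serious adverse events as those not related to COVID-19.

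Section 13.1 nevertheless states "It is not expected that any patient will be lost to follow-up, even if discharged home", and plans Kaplan-Meier plots of survival by arm.

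**The concern.** The endpoint is narrower than the question it answers. A death at home on day 20 happens while the participant is on study, yet it is not counted.

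The exclusion is not neutral between arms. Whether a death can count depends on whether the patient is still in hospital. Discharge may be affected by favipiravir itself or, because allocation is known, by the decisions of treating staff. Discharge is also one of the events that completes the primary endpoint. A patient sent home on day 6 who dies there on day 12 is therefore an improvement in the primary analysis and not a death in item 3. Both effects favour the arm that discharges sooner.

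Widening the endpoint in the analysis would not be enough, because the protocol does not secure vital status at day 28 for people who have left hospital. An analysis plan cannot recover data that were never collected.

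**Working it through.** The protocol states no figure for this point: no mortality rate, no distribution of discharge times, no share of deaths after discharge. The check has two parts, a comparison of sections and an illustration on assumed inputs.

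**1. Contact after discharge, by day of discharge**

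| Discharged | Telephone interview (10.3) | Return for samples (10.4) | Bloods (9.4) |
|---|---|---|---|
| Before day 5 | Yes, day not stated | Two, if well enough | Day 5-10 and day 14-28 visits |
| Days 5-9 | Yes, day not stated | One in days 14-28, if well enough | Day 14-28 visit (and day 5-10 if not yet done) |
| Days 10-13 | No | One in days 14-28, if well enough | Day 14-28 visit |
| Days 14-27 | No | None requested | Day 14-28 visit mentioned, with no cut-off by discharge day |

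Two routes apply to everyone to day 28: readmission data (10.2) and non-COVID-19 adverse events (12.6). A death during a readmission is still in hospital, so item 3 can count it. A non-COVID-19 death at home is a reportable serious event.

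What remains is a COVID-19 death at home without readmission. It is outside item 3, outside the serious adverse event definition in 12.4, and not captured by a visit that only patients who are well enough attend. No row has a fixed vital-status check at day 28.

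The ordinal score has a related gap. Categories 1 and 2 differ by whether normal activities have resumed, which takes contact to establish. Patients discharged on days 10 to 13 get no call, and their return may fall anywhere in days 14 to 28, so the day-14 score is not secured.

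**2. Illustration of the bias**

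Inputs: 250 per arm (13.2). Assumed: true 28-day mortality *p*, equal in both arms, from 10 to 20%; share of deaths occurring after discharge and not counted, *s*, of 5% in control and 10 to 20% in the favipiravir arm.

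Observed in-hospital mortality in an arm is *p*(1 − *s*), so the apparent risk ratio is (1 − *s*_fav)/(1 − *s*_ctl), whatever *p* is:

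- 10% against 5%: 0.90/0.95 = 0.947
- 20% against 5%: 0.80/0.95 = 0.842

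The spurious difference in deaths is 250 × *p* × (*s*_fav − *s*_ctl):

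- smallest: 250 × 0.10 × 0.05 = 1.25
- largest: 250 × 0.20 × 0.15 = 7.5

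If the shares are equal in the two arms, the ratio is unbiased and only precision is lost. For example, true mortality of 20% against 12% has power of about 69% (two-sided alpha 0.05, normal approximation). If 20% of deaths in each arm go uncounted, the comparison becomes 16% against 9.6% and power is about 57%.

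**The case against.** In-hospital mortality is an ordinary endpoint for a trial in inpatients, and here it is one of 14 unranked secondary items. The missing horizon is mostly a missing label, since collection and participation both end at day 28. These points stand, and they limit the weight of the finding.

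Several stronger readings are tempting, and the protocol does not support them:

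- *Deaths and events after discharge are simply missed.* Readmissions are followed to day 28, non-COVID-19 adverse events are reportable to day 28, and those discharged before day 14 are asked back. The gap is chiefly COVID-19 deaths at home.
- *Patients discharged on days 14 to 27 have no scheduled contact.* Section 10.4 asks nothing further of them, but section 9.4 refers to bloods at the day 14-28 visit without excluding them.
- *Mortality is a key secondary endpoint.* The protocol does not rank it. It is the only endpoint confined to mortality.
- *The collection schedule contradicts 12.6 and 13.1.* The first sets a reporting duty and the second states an expectation. The absence of a dedicated call makes that expectation optimistic; it does not contradict either.

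The magnitude can also be attacked, because it comes wholly from the assumed difference in post-discharge shares. That is correct, and the calculation shows direction and scale only. It does not remove the structural problem: what counts as a death depends on a discharge decision made with the allocation known.

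**Conclusion.** The point holds. The mortality objective is unrestricted, the only mortality endpoint is confined to hospital, and a death at home before day 28 is excluded by definition. The exclusion can favour the arm that discharges sooner. Ascertainment after discharge is incomplete, chiefly for COVID-19 deaths at home, which makes the expectation of no loss to follow-up, and any survival plot that relies on it, optimistic.

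The true size is unknown. The illustrated risk ratios of about 0.95 to 0.84, or roughly 1 to 8 deaths at 250 per arm with no real effect, rest on assumed shares and assumed mortality. A reader should not infer that a bias of this size is present, or that the trial loses sight of patients once they go home; the protocol supports neither. This is an inexpensive improvement to a secondary endpoint and does not affect the validity of the design as a whole.

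**What to change.** In 6.4, add all-cause mortality to day 28 after randomisation, in or out of hospital, as the endpoint for the mortality objective, and keep in-hospital mortality as supportive. Adding is safer than replacing: enrolment began in May 2020, this version is dated April 2021, and the allocation is open.

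In 10.3, extend the existing telephone interview, or a record check, from discharges before day 10 to all participants discharged before day 28. Fix the timing: vital status at day 28 for everyone, and the ordinal score at day 14 for those already home.

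The cost is a protocol amendment, one or two short calls or record checks per discharged participant, and retrospective record checks for those who have already exited. No treatment rule changes.

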#### 8.2. Inclusion Criteria

The participant may enter the study if the following apply:

- 1. Adult participants: Signed informed consent or documented and witnessed oral informed consent
- 2. New admission to hospital for period expected to last  $\geq 1$  night
- 3. Suspected or confirmed COVID-19 infection

Patients are suspected of COVID-19 infection if they have the following:

Influenza like illness (fever ≥37.8°C or patient reported history of fevers and at least one of
the following respiratory symptoms, which must be of acute onset: persistent cough,
hoarseness, nasal discharge or congestion, shortness of breath, sore throat, wheezing or
sneezing).

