#### 10. PARTICIPANT ASSESSMENTS

#### 10.1. Baseline Data Collection

The following information will be collected:

- Demographics
- Co-morbidities
- Medication history and allergy
- Date of COVID-19 symptom onset
- Date of confirmatory COVID-19 test (SARS-CoV-2 infection by PCR or other National standard)
- Smoking status
- Travel history for preceding 6 months
- Clinical parameters (Heart rate, Respiratory rate, Oxygen Saturations)
- Baseline bloods (Full blood count, C-reactive protein, procalcitonin (if this is not part of site
  routine testing it is not required by protocol), ferritin, urea, d-dimer, LDH, troponin, urea &
  electrolytes, liver function (if available)

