## **20. APPENDIX A: NEWS2**

Physiological	Score 3 2 1 0 1 2 3						
parameter	3	- 4	'		'	- 4	3
Respiration rate (per minute)	≤8		9–11	12-20		21–24	≥25
SpO 2 Scale 1 (%)	≤91	92–93	94–95	≥96			
SpO 2 Scale 2 (%)	≤83	84–85	86–87	88-92 ≥93 on air	93–94 on oxygen	95–96 on oxygen	≥97 on oxygen
Air or oxygen?		Oxygen		Air			
Systolic blood pressure (mmHg)	≤90	91–100	101–110	111–219			≥220
Pulse (per minute)	≤40		41–50	51–90	91–110	111–130	≥131
Consciousness				Alert			CVPU
Temperature (°C)	≤35.0		35.1–36.0	36.1–38.0	38.1–39.0	≥39.1	

Figure 3 The NEWS2 Scoring system(11)

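### A 2-point fall in a single NEWS2 component is impossible for anyone scoring 0 or 1 at randomisation, and the saturation component can count starting oxygen as a response

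*Protocol*

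**What the plan says.** Protocol section 6.4 lists two NEWS2 endpoints among its secondary outcomes. Endpoint 4 is "Time to 2 point reduction (maintained for 24 hours) in total NEWS2". Endpoint 5 is "Time to 2 point reduction (maintained for 24 hours) in the NEWS2 (National Early Warning Score 2) component compared to baseline NEWS2", with the baseline taken at randomisation, to be computed for each of temperature, heart rate, respiratory rate and oxygen saturations. Neither is limited to participants with any minimum baseline score.

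Appendix A ("The NEWS2 Scoring system") gives each physiological item a score from 0 to 3, with bands running 3, 2, 1, 0, 1, 2, 3 from low to high values. Two of the rows read "Temperature (°C) ≤35.0 35.1–36.0 36.1–38.0 38.1–39.0 ≥39.1" and "Pulse (per minute) ≤40 41–50 51–90 91–110 111–130 ≥131". Whether the patient is on air or oxygen has a row of its own: 2 points for oxygen, 0 for air. SpO2 Scale 1 is scored without regard to that row.

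Section 8.2 sets no minimum NEWS2 or vital sign for entry. The fever criterion for suspected cases is "fever ≥37.8°C or patient reported history of fevers". Section 13.1 puts all analyses on an intention-to-treat basis and refers to the statistical analysis plan for other secondary analyses.

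**The concern.** A 2-point threshold suits a total score with a wide range. Applied to a single item that runs only from 0 to 3, it meets a floor: a baseline of 0 or 1 leaves no room to fall by 2. These participants are structural non-events, whatever the treatment does. If they stay in the analysis, they pull both arms towards the same low cumulative incidence.

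The saturation component raises a second issue, one of direction. Oxygen raises the measured saturation, and the row that would register its use is not in the component. A participant who deteriorates enough to need oxygen can then be recorded as improved, and one who comes off oxygen at an unchanged saturation is not. On the primary seven-category scale, starting oxygen is a worsening, from category 3 to category 4. Two outcomes in the same trial would score the same event in opposite directions.

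**Working it through.** The protocol states no event rate or power for these endpoints, so there is no figure to reproduce.

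**1. Who can have the event (Appendix A).** A fall of 2 needs a baseline component score of at least 2.

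| Component | Score 0 or 1: event impossible | Score 2 or 3: event possible |
|---|---|---|
| Temperature, °C | 35.1–39.0 | ≥39.1 or ≤35.0 |
| Pulse, per minute | 41–110 | ≥111 or ≤40 |
| Respiratory rate, per minute | 9–20 | ≥21 or ≤8 |
| SpO2 Scale 1, % | ≥94 | ≤93 |

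A participant who meets the fever criterion at 37.8°C scores 0. For respiratory rate the table goes straight from 0 to 2 at 21 per minute, so every participant at 21 or above can respond.

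**2. What share that might be.** The protocol gives no baseline vital signs. The means and SDs below are therefore assumptions, with normal distributions. For temperature, share able to respond = 1 − Φ((39.05 − μ)/σ) + Φ((35.05 − μ)/σ); the other components follow the same pattern.

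| Component | Assumed mean | Assumed SD | Share able to respond |
|---|---|---|---|
| Temperature | 37.2–38.2 | 0.7–1.1 | 0.5%–22% |
| Pulse | 80–100 | 14–18 | 2%–28% |
| Respiratory rate | 19–26 | 4–6 | 36%–92% |
| SpO2 Scale 1 | 92–96 | 2–4 | 11%–77% |

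At the top of the range, temperature (μ = 38.2, σ = 1.1) gives 1 − Φ(0.773) + Φ(−2.864) = 0.220 + 0.002 = 0.222. Pulse (μ = 100, σ = 18) gives 1 − Φ(0.583) plus a negligible lower tail = 0.280. So at least 78% could not respond on temperature and at least 72% could not on pulse.

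**3. What that does to power.** Schoenfeld approximation, two-sided alpha 0.05, 1:1: power = Φ(√d/2 × ln(HR) − 1.96), with d events. Assume a subhazard ratio of 1.5 among those able to respond, 80% of whom have the event.

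- All 500 able to respond: d = 400; 10 × 0.405 − 1.96 = 2.09; power 98%.
- 10% able to respond, analysed alone (50 participants): d = 40; 3.162 × 0.405 − 1.96 = −0.68; power about 25%.
- The same 10%, with the other 450 kept in. An 80% average event proportion with a ratio of 1.5 means about 73.6% in control and 1 − (1 − 0.736)^1.5 = 86.4% on favipiravir. Over everyone randomised this becomes 7.36% against 8.64%. The apparent ratio is ln(1 − 0.0864)/ln(1 − 0.0736) = 1.18. With d = 40, 3.162 × 0.168 − 1.96 = −1.43; power about 8%.

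The shortage of events is one loss, and keeping the structural non-events adds another.

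**4. The saturation component (Scale 1).**

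| Change | SpO2 item alone | SpO2 plus oxygen row |
|---|---|---|
| 88% air → 94% oxygen | −2 (response) | 0 |
| 91% air → 96% oxygen | −3 (response) | −1 |
| 93% air → 96% oxygen | −2 (response) | 0 |
| 94% air → 96% oxygen | −1 | +1 |
| 96% oxygen → 96% air | 0 (no response) | −2 (response) |

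The false response needs a baseline of 93% or less on air and the higher value held for 24 hours. On Scale 2 it needs a baseline of 85% or less, for example 84% on air to 90% on oxygen, which gives −2. Endpoint 4 is largely protected, because the total includes the oxygen row.

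**The case against.** The strongest reply is that the risk set for a secondary analysis is ordinary content for the statistical analysis plan, which is not at hand, and that intention to treat does not forbid a subset fixed at baseline. That is fair for the risk set. It does not cover the threshold or the list of components: the protocol itself fixes both, and they produce the floor and the oxygen problem when followed as written.

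Structural non-events also fall in both arms, so they dilute the comparison and do not bias it. That stands. A 2-point threshold may be a deliberate guard against trivial changes such as pulse 91 to 90. That also stands, and it is a reason to keep the threshold and restrict who is analysed.

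Starting oxygen is captured elsewhere, by the primary scale and by endpoints 4, 10 and 11. This limits the damage but does not make the saturation component right.

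A reader might infer more than the documents support:

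- **Most participants are excluded on all four components.** There is no baseline distribution in the protocol, and for respiratory rate most participants may well be able to respond.
- **The endpoints cannot show an effect.** Little power is not none.
- **The saturation endpoint will favour the wrong arm.** That would need oxygen starts to differ between arms, which nothing in the documents shows.
- **NEWS2 cannot be computed at baseline, because section 10.1 names only "Clinical parameters (Heart rate, Respiratory rate, Oxygen Saturations".** Endpoint 5 itself calls for a NEWS2 at randomisation, and section 10.2 collects all routine inpatient data from day 0. At most the list needs tidying.

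**Conclusion.** The point holds in two parts, of different certainty.

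The floor is arithmetic on the protocol's own table: nobody with a component score of 0 or 1 at randomisation can have the event. That this excludes most participants is probable for temperature and heart rate (72% or more over the assumed ranges), not established for saturation (23% to 89% excluded) and doubtful for respiratory rate (8% to 64%). The power figures of 98%, 25% and 8% illustrate the scale of the loss and rest on the assumed 10% share, 80% event proportion and subhazard ratio of 1.5. Endpoint 4 has the same floor at a total of 0 or 1, but the documents give no basis for sizing it.

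The saturation component can record starting oxygen as a response and miss weaning from it, contrary to the primary scale. This is certain as a scoring rule but conditional in practice: it needs a low baseline saturation on air and 24 hours at the higher value.

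These are secondary endpoints. The primary endpoint, its analysis and N = 500 are untouched.

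**What to change.** Keep the 2-point threshold and state three things in section 6.4 or the statistical analysis plan:

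1. Each endpoint 5 component is analysed among participants whose baseline score on that component is at least 2.
2. Endpoint 4 is analysed among participants whose baseline total NEWS2 is at least 2.
3. The saturation component is the sum of the SpO2 item and the air-or-oxygen item, and its risk set is defined by that sum. Starting oxygen then lowers the score by at most 1 (3 on air to 0 + 2 on oxygen), so it cannot count as a response. Weaning at a steady 96% lowers it by 2 and does count.

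Report the number at risk for each component by arm. Where that number is small, present the result as descriptive: restriction removes the dilution but creates no events.

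The cost is wording only, since the observations are routine ward data. The denominator will differ between components, but it is fixed at baseline, so each comparison stays randomised. One limit remains: the oxygen item does not grade the amount of oxygen, so a participant already on oxygen whose saturation rises from 91% to 96% after an increase still scores −3 on either definition. The report should say so.
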